Visit*	1	2	3*	4	5	6	7	8	9	10	11	12	13	14	15	16	17	18	19	20	21	99*	ED*	801*
Week of Treatment	-2	-1	0	4	8	12	16	20	24	28	32	36	40	44	48	52	56	60	64	68	72	72		4 wks Post TxP
Allowable Deviation (days)*		±3	±3	±3	+7	±3	+7	±3	±3	±3	±3	+7	±3	±3	±3	±3	±3	±3	±3	±3	±7	±7		±3
Fasting Visit*	X	X	X	X	X	X	X	X	X			X			X			X			X	X	X	X
Telephone Visit										X	X		X	X		X	X		X	X				
2-hour oral glucose tolerance test (includes glucose, insulin, c-peptide at each timepoint)*		X																			X		X	
Chemistry panel (include Cr for eGFR calculation and glucose)*	X		X			X			X			X			X			X			X		X	X
Lipid panel	X		X						X												X		X	X
Fasting insulin						X			X			X			X			X			X		X	X
C-peptide						X			X			X			X			X			X		X	X
Free fatty acids	X		X						X												X		X	X
Urinary albumin/creatinine	X*								X												X		X	X
Cystatin-c	X*								X												X		X	X
Calcitonin	X*					X			X												X		X	X
Hematology	X*					X			X												X		X	X
HbA1c	X		X			X			X			X			X			X			X		X	X
Pancreatic amylase, lipase	X		X			X			X												X		X	X
Thyroid-stimulating hormone	X*																							
Immunogenicity (includes PK sample)*			X	X		X			X						X						X		X	X
TZP PK*					X		X					X												
Pharmacogenetic stored sample			X																					

Visit*	1	2	3*	4	5	6	7	8	9	10	11	12	13	14	15	16	17	18	19	20	21	99*	ED*	801*
Week of Treatment	-2	-1	0	4	8	12	16	20	24	28	32	36	40	44	48	52	56	60	64	68	72	72		4 wks Post TxP
Allowable Deviation (days)*		±3	±3	±3	+7	±3	+7	±3	±3	±3	±3	+7	±3	±3	±3	±3	±3	±3	±3	±3	±7	±7		±3
Fasting Visit*	X	X	X	X	X	X	X	X	X			X			X			X			X	X	X	X
Telephone Visit										X	X		X	X		X	X		X	X				
Nonpharmacogenetic stored sample			X			X			X						X						X		X	X
Mental Health Questionnaires																								
PHQ-9*	X		X			X			X			X			X			X			X	X	X	X
C-SSRS (Baseline/Screening Version)*	X																							
C-SSRS (Since Last Visit Version)*		X	X	X	X	X	X	X	X	X	X	X	X	X	X	X	X	X	X	X	X	X	X	X
Self-Harm Supplement Form*	X	X	X	X	X	X	X	X	X	X	X	X	X	X	X	X	X	X	X	X	X	X	X	X
Self-Harm Follow-up Form*	X	X	X	X	X	X	X	X	X	X	X	X	X	X	X	X	X	X	X	X	X	X	X	X
Patient Reported Outcomes																								
PGIS			X																			X	X	
SF-36, version 2, acute form			X																			X	X	
IWQOL-Lite CT			X																			X	X	
EQ-5D-5L			X																			X	X	

1.3.2. Schedule of Activities for additional 2-year treatment period for participants with prediabetes at randomization

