4.1.1.2.4. Early Discontinuation of Treatment Visit

Participants unable or unwilling to continue the study treatment for any reason will perform an early discontinuation of treatment (ED) visit. If the participant is discontinuing during an unscheduled visit, that visit should be performed as the ED visit. If the participant is discontinuing during a scheduled visit, that visit should be performed as an ED visit. Procedures should be completed according to the Schedule of Activities (Section 1.3). Patient-reported outcomes questionnaires should be administered as early as possible, as per Suggested Visit Structure (Section 10.8). Administration of mental health questionnaires should follow assessment for AEs (see Section 7.2).

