6.1. Populations for Analyses

For purposes of analyses, [Table GPHK.6.1](#) defines the analysis sets.

Table GPHK.6.1. Description of Analysis Datasets

Analysis Set	Description
Entered Participants	All participants who sign informed consent
Randomized Participants	All participants who are randomly assigned a study treatment
Modified Intent-to-Treat (mITT)	All randomly assigned participants who are exposed to at least 1 dose of study drug. Participants will be included in the treatment group they were randomized to.
Efficacy Analysis Set (EAS)	Data obtained during treatment period from mITT, excluding data after discontinuation of study drug (last dose date + 7 days).
Full Analysis Set (FAS)	Data obtained during treatment period from mITT, regardless of adherence to study drug.
Safety Analysis Set (SS)	Data obtained during the treatment period plus safety follow-up period from mITT, regardless of adherence to study drug.

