Table GPHK.6.2. Baseline and Postbaseline Definitions for Safety Groups

Analysis Set	Analysis Type	Baseline	Postbaseline
SS	1.1) Treatment-Emergent Adverse Events	The baseline period is defined as the start of screening and ends prior to the first dose of study treatment (typically at Week 0).	Starts after the first dose of study treatment and ends at the end of the study period (including off-drug follow up visit).
SS	1.2) Treatment-Emergent Abnormal Labs ^a , Vital Signs, and ECGs.	Baseline will include all scheduled and unscheduled measurements during the baseline period (Visit 1 to Visit 3)	Postbaseline will be defined as measurements after Visit 3 . All scheduled and unscheduled measurements will be included.
SS	1.3) Change from Last Baseline to Week xx and to Last Postbaseline for Labs ^a , Vital Signs, and ECGs.	The last scheduled and unscheduled non-missing assessment recorded during the baseline period defined above (1.2).	Postbaseline will be defined as above (1.2). Only scheduled visits will be included. The early discontinuation (ED) visits are considered scheduled visits.

Abbreviations: ECGs = electrocardiogram; SS = Safety Analysis Set.

^a Immunogenicity related analysis is specified in Section [6.14.3.7](#).

There will be 2 estimands of interest in evaluating primary and key secondary efficacy objectives:

- For objectives controlled for Type 1 error at 72 weeks:
 - the “efficacy” estimand, defined as the average treatment effect of tirzepatide relative to placebo at 72 weeks, as an adjunct to a reduced-calorie diet and increased physical activity, in the randomized participants had they remained on their randomized treatment for the entire planned 72 weeks treatment duration.
 - the “hybrid” estimand, is the average treatment effect of tirzepatide relative to placebo at 72 weeks, as an adjunct to a reduced-calorie diet and increased physical activity, for the randomized participants regardless of the adherence to treatment

- For objectives controlled for Type 1 error assessed after 72 weeks:
 - the “efficacy” estimand, defined as the treatment effect of tirzepatide relative to placebo at 176/193 weeks, as an adjunct to a reduced-calorie diet and increased physical activity, in the randomized participants with prediabetes at randomization had they remained on their randomized treatment for the entire planned 176 weeks treatment duration.

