6.4. Handling of Dropouts or Missing Data

For the primary and key secondary efficacy endpoint analyses subject to type 1 error rate control, data for participants with missing values at the 72-week visit (or weight related measurements at

176-week visit for participants with prediabetes at randomization) will be imputed based on the method described in Section 6.13.1.3. However, for the parameters with only 1 postbaseline measure during the analysis period per schedule of activity, the last observation carried forward (LOCF) approach will be applied to impute the endpoint when ED measure is available.

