6.13.2. Secondary Efficacy Analyses Subject to Type 1 Error Rate Control

Table GPHK.6.4. Secondary Measures Controlled for Type 1 Error

Objectives	Relative to the efficacy measure:	Analysis conducted in a manner similar to	Additional Information
Tirzepatide 10 mg and 15 mg combined is superior to placebo:	Mean change in body weight (kg) from randomization at 20 weeks	MMRM model in Section 6.13.1.1 for efficacy estimand and ANCOVA model in Section 6.13.1.2 for hybrid estimand	
Tirzepatide 5 mg is superior to placebo:	Mean percent change in body weight from randomization and percentage of participants achieving at least 5% body weight reduction at 72 weeks	Section 6.13.1.1 for efficacy estimand and Section 6.13.1.2 for hybrid estimand	
Tirzepatide 10 mg and/or 15 mg is superior to placebo:	Percentage of participants achieving body weight reduction $\geq 10\%$, $\geq 15\%$ and $\geq 20\%$ at 72 weeks	logistic model in Section 6.13.1.1 for efficacy estimand and logistic model in Section 6.13.1.2 for hybrid estimand	
	Mean change in waist circumference (cm) from randomization at 72 weeks	MMRM model in Section 6.13.1.1 for efficacy estimand and ANCOVA model in Section 6.13.1.2 for hybrid estimand	LSM estimates will be plotted by treatment through 72-weeks.

Secondary Measures Controlled for Type 1 Error

Objectives	Relative to the efficacy measure:	Analysis conducted in a manner similar to	Additional Information
Tirzepatide 10 mg and 15 mg combined is superior to placebo	Mean change in SF-36 v2 acute form Physical Functioning domain score from randomization at 72 weeks	ANCOVA model with the terms of treatment group, stratification factors as fixed effects, and baseline SF-36 v2 acute form Physical Functioning domain score as a covariate.	For efficacy estimand, missing data will be imputed based on LOCF method. For hybrid estimand, missing data will be imputed based on Section 6.13.1.3.
Tirzepatide (all doses combined) is superior to placebo:	Mean change in triglycerides, HDL-C, non-HDL-C, SBP and fasting insulin from randomization at 72 weeks	MMRM model in Section 6.13.1.1 for efficacy estimand and ANCOVA model in Section 6.13.1.2 for hybrid estimand	For hybrid estimand, missing data will be imputed first for each treatment based on Section 6.13.1.3, then combine all tirzepatide doses.

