Appendix 1. Body Composition Assessments via Dual-Energy X-ray Absorptiometry (DXA)

This section is applicable to the participants who are enrolled in the Dual Energy X-ray Absorptiometry (DXA) addendum.

The primary objective of DXA addendum is to demonstrate that tirzepatide (5 mg, 10 mg, and 15 mg combined) QW is superior to placebo in percent change in total body fat mass from baseline to 72 weeks.

Percent change of total body fat mass will be calculated as:

$$\left[\frac{\text{Total body fat mass at 72 weeks} - \text{Total body fat mass at baseline}}{\text{Total body fat mass at baseline}} \right] * 100$$

The secondary objectives include

- To demonstrate that tirzepatide (5 mg, 10 mg, and 15 mg combined) QW is superior to placebo in loss of total body fat mass in kg from randomization to 72 weeks, and
- To assess, for tirzepatide (5 mg, 10 mg, and 15 mg combined) QW, the following parameters, measured at randomization and 72 weeks:
 - Percent change in total body lean mass, and
 - change in total body lean mass in kg.

Percent change of total body lean mass will be calculated as:

$$\left[\frac{\text{Total body lean mass at 72 weeks} - \text{Total body lean mass at baseline}}{\text{Total body lean mass at baseline}} \right] * 100$$

DXA will be performed at the baseline and at the end of 72-week treatment (Visit 21) or ED.

In addition to the primary and secondary outcomes listed above, the following parameters will also be analyzed:

- total body mass (kg)
- total body fat mass (kg)
- total body lean mass (kg)
- percent body fat mass = total body fat mass / total body mass * 100
- percent body lean mass = total body lean mass / total body mass * 100
- fat lean mass ratio = total body fat mass / total body lean mass
- fat lean mass loss ratio = total body fat mass change / total body lean mass change, and
- fat lean mass percent loss ratio = percent change of total body fat mass / percent change of total body lean mass.

Unless otherwise specified, all analyses for the variables measured or derived from DXA will be conducted on all participants who are enrolled in this addendum, randomized, and have at least 1 dose of study drug, with both baseline and at least 1 postbaseline measurement. Baseline is defined as the last non-missing data collected at randomization (prior to first dosing of study drug). Missing data at Week 72 will be imputed using the last observation carried forward method.

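### Under the efficacy estimand, missing Week 72 SF-36 Physical Functioning is filled with the score at stopping, not the on-treatment Week 72 value the estimand asks for

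*SAP*

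**What the plan says.** SAP 6.2 defines the 72-week efficacy estimand as the average effect "in the randomized participants had they remained on their randomized treatment for the entire planned 72 weeks treatment duration". SAP 6.1 restricts the Efficacy Analysis Set (EAS) accordingly: "Data obtained during treatment period from mITT, excluding data after discontinuation of study drug (last dose date + 7 days").

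Table GPHK.6.4 (SAP 6.13.2) analyses change in SF-36 PF, pooled 10 mg and 15 mg against placebo, by ANCOVA. On missing values it says: "For efficacy estimand, missing data will be imputed based on LOCF method". For the hybrid estimand it refers to SAP 6.13.1.3 instead.

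SAP 6.4 says what is carried. For parameters with a single scheduled postbaseline measure, "the last observation carried forward (LOCF) approach will be applied to impute the endpoint when ED measure is available". In Protocol 1.3.1 the row "SF-36, version 2, acute form" has a baseline assessment, one at Week 72 and one at ED, with none between. Protocol 4.1.1.2.4 fixes when the ED score is taken: "Participants unable or unwilling to continue the study treatment for any reason will perform an early discontinuation of treatment (ED) visit".

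The other controlled continuous 72-week endpoints (percent weight change, waist circumference, lipids, systolic pressure, fasting insulin) use MMRM for this estimand. The responder endpoints dichotomise Week 72 weights predicted from an MMRM.

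**The concern.** The estimand asks what PF would have been at Week 72 on continued treatment. The rule supplies what PF was on the day treatment stopped, which may be well before Week 72 and possibly during the 20-week dose escalation. It then enters that value into the ANCOVA as if it had been observed at Week 72, with no allowance for not knowing the Week 72 value.

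The hypothesis for this endpoint (H1015,12 in SAP 6.13.3) is within the Type 1 error control strategy. SAP 6.13 uses the efficacy estimand for regulators other than the FDA, for publications and for other purposes. A controlled claim in those settings would therefore rest on an estimator aimed at a different quantity from the one declared. The sensitivity analyses in SAP 6.13.1.4 cover only the primary outcomes, so nothing planned would show how much the choice matters.

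**Working it through.** The documents give no planned effect, SD of change, power or missing-data rate for SF-36 PF, so there is no stated figure to reproduce. The check has four steps.

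**1. What is carried forward.** There is no SF-36 between baseline and Week 72 other than at ED, so the last postbaseline observation for someone who stops early is the ED score. It qualifies only if taken within 7 days of the last dose, because later data are outside the EAS. A Week 72 score collected after stopping is also outside the EAS. The SAP does not say what happens to participants with no usable ED score.

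**2. When this equals the estimand.** Let *g* be an arm's mean Week 72 change on treatment, *d* the share carried forward, and *f* the fraction of *g* reached at the ED visit. Assume every other participant contributes an on-treatment Week 72 score.

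- LOCF arm mean = *g* × [1 − *d*(1 − *f*)]
- LOCF contrast = *g*T[1 − *d*T(1 − *f*T)] − *g*P[1 − *d*P(1 − *f*P)]
- Estimand = *g*T − *g*P

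These agree if *f* = 1 in both arms, or if the two arms' errors happen to cancel.

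**3. Illustrative size.** The only document input is the 25% planning dropout rate in Protocol 9.2, which is not given by arm and is not a share carried forward. The 15%, the values of *f* and the gains are assumptions. With equal *d* and equal *f* in both arms, attenuation = *d*(1 − *f*):

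| Share carried | *f* = 0.25 | *f* = 0.5 | *f* = 0.75 |
|---|---|---|---|
| 15% | 11.25% | 7.5% | 3.75% |
| 25% | 18.75% | 12.5% | 6.25% |

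With unequal dropout the sign is not fixed. Suppose both arms would gain 2 points on treatment (no true effect) and *f* = 0.5:

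- 15% tirzepatide, 35% placebo: 2(1 − 0.075) − 2(1 − 0.175) = 1.85 − 1.65 = +0.20, favouring tirzepatide.
- 30% tirzepatide, 20% placebo: 2(1 − 0.15) − 2(1 − 0.10) = 1.70 − 1.80 = −0.10, favouring placebo.

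**4. Precision under the alternative.** With 1200 against 600 participants and an assumed SD of 10, the full-data SE is 10 × √(1/600 + 1/1200) = 0.50. With 25% missing and predictors that carry no information, imputation raises the SE by at most about 1/√0.75 = 1.155, to 0.577. For an assumed true difference of 1.5 points at two-sided 0.05:

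- LOCF with *f* = 0.5: expected estimate 1.5 × 0.875 = 1.3125; 1.3125/0.50 = 2.625; power about 0.75.
- Imputation: 1.5/0.577 = 2.60; power about 0.74.

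With SD 7 both are about 0.96. The case for changing the method is alignment with the estimand, not power.

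**The case against.** The strongest defence is that the design drove the choice. With one scheduled postbaseline SF-36, the MMRM used for the other continuous endpoints is not available in the same way, and SAP 6.4 sets a general rule for such parameters. LOCF also uses the only on-treatment postbaseline PF score that an early stopper has. This explains the choice, but it does not make the stopping score an estimate of the Week 72 score. Nor can the ED score simply be added as a predictor of Week 72 PF: within the EAS nobody has both an ED score and an on-treatment Week 72 score from which to learn the relation.

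The defence is right on scope. Table GPHK.6.4 sends the hybrid (FDA) analysis to SAP 6.13.1.3, so that analysis is unaffected.

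Four stronger readings are tempting and are not supported:

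- **That Type 1 error control for H1015,12 is broken.** Inflation is possible: the 15% against 35% example gives about 0.07 (SD 10) or 0.09 (SD 7) at a nominal 0.05. It rests on an assumed dropout gap, and the documents give no rates by arm.
- **That 15–25% is the expected share carried forward.** ED scores outside the 7-day window are excluded, so the share could be well below the dropout rate.
- **That ED scores are typically taken during adverse events.** The ED visit applies to stopping for any reason.
- **That LOCF in the DXA addendum (SAP Appendix 1) is the same fault.** That analysis has its own population, no stated efficacy estimand and no multiplicity adjustment.

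**Conclusion.** The point holds as a mismatch between estimand and estimator, confined to SF-36 PF under the efficacy estimand. It follows from the text of SAP 6.2, SAP 6.4, Table GPHK.6.4 and the schedule, and needs no numerical assumption. LOCF would be adequate if PF would not change between stopping and Week 72, but the SAP gives no reason to expect that. Protocol 4.2 justifies the 72-week duration, with at least 52 weeks at the dose achieved, as what is needed to see the full effect on body weight. That concerns weight rather than PF, but it makes constancy after an early stop hard to presume.

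The size is uncertain. The 7.5–12.5% attenuation is an illustration that assumes equal shares carried and equal fractions realised in both arms, with half the change realised at stopping. If either differs by arm the bias can go in either direction, so LOCF cannot be defended as reliably conservative, nor shown to be anti-conservative.

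**What to change.** In Table GPHK.6.4, for the efficacy estimand only:

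- Replace LOCF with multiple imputation of Week 72 PF within each randomized arm, under missing at random, from participants with an on-treatment Week 72 score. Predictors: baseline PF, the stratification factors and on-treatment weight change.
- Apply it to everyone in the analysis without an on-treatment Week 72 score, including those with no usable ED score. Then pool the 10 mg and 15 mg arms, fit the planned ANCOVA and combine by Rubin's rules.
- Keep LOCF of the ED score, where it falls within 7 days of the last dose, as a sensitivity analysis. State how participants without such a score are handled in it.
- Amend the LOCF sentence in SAP 6.4, which names no estimand, so that it agrees with the table.

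The cost is modest. Weight is already measured repeatedly and the SAP already uses multiple imputation with Rubin's rules, so the extra programming is small. Intervals will be wider, by at most about 15% at 25% missing, and by less if weight change predicts PF. The imputation rests on missing at random, which should be stated.

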9.2. Sample Size Determination

Approximately 3429 participants will be screened to achieve 2400 randomly assigned to study intervention (600 participants per intervention group).

The sample size determination assumes that evaluation of superiority of 10-mg tirzepatide and tirzepatide 15 mg to placebo will be conducted in parallel, each at a 2-sided significance level of 0.025 using a 2-sample t-test. Additionally, a difference of at least 11% mean body weight percentage reduction from randomization at 72 weeks for 10-mg tirzepatide and/or tirzepatide 15 mg compared with placebo, a common SD of 10%, and a dropout rate of 25% are assumed for statistical power calculations. Under the assumptions above, randomizing 2400 participants in a 1:1:1:1 ratio to tirzepatide 5 mg (600), tirzepatide 10 mg (600), tirzepatide 15 mg (600), and placebo (600) provides more than 90% power to demonstrate superiority of tirzepatide 10 mg and/or 15 mg to placebo.

The chosen sample size and randomization ratio also provides >90% power to establish superiority of 10-mg tirzepatide and 15-mg tirzepatide doses to placebo in term of percentage of participants achieving at least 5% body weight reduction at 72 weeks, conducted in parallel using a Fisher's exact test, each at a 2-sided significance level of 0.025, assuming 25% placebo-treated participants and 90% tirzepatide-treated participants achieving the goal and a dropout rate of 25%.

In addition, assuming that approximately 60% of the randomized population will have prediabetes, the study sample size will also provide more than 90% power to demonstrate superiority of tirzepatide (all doses combined) over placebo in terms of delaying the onset of diabetes for participants with prediabetes at study entry. It is based on the following assumptions: 1.6% (corresponding to annual hazard rate of 0.54%) of participants randomized to tirzepatide and 6% of participants randomized to placebo (corresponding to annual hazard rate of

2.1%) will progress to diabetes during the 3-year period; 49% of participants will drop out (corresponding to annual drop-out rate of 22%) during the same period; and the test will be conducted at a 2-sided significance level of 0.05.

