6.2. General Considerations

Statistical analysis of this study will be the responsibility of Eli Lilly and Company (Lilly) or its designee. Some analyses and summaries described in this analysis plan may not be conducted if not warranted by data (for example, few events to justify conducting an analysis). Additional analyses of the data may be conducted as deemed appropriate.

Unless otherwise noted, tests of treatment effects will be conducted at a 2-sided alpha level of 0.05, and the confidence interval (CI) will be calculated at 95% 2-sided.

Unless specified otherwise, efficacy and safety will be assessed using the modified intention-to-treat (mITT) population, and data will be analyzed based on the randomized treatment (that is, not the actual treatment received by the participant). For submission of Study GPHK to the US Food and Drug Administration (FDA) to support the registration of tirzepatide for chronic weight management, the primary efficacy analysis will be conducted using Full Analysis Set (FAS). For other purposes, the efficacy analysis will be conducted using Efficacy Analysis Set (EAS). Safety analysis will be conducted using Safety Analysis Set (SS).

Summary descriptive statistics for continuous measures will include sample size, mean, standard deviation (SD), median, minimum, and maximum. The analysis model to make comparisons among treatment groups relative to continuous measurements assessed over time will be either analysis of covariance (ANCOVA) or a mixed model for repeated measures (MMRM).

Kaplan-Meier method will be used for estimation of cumulative event-free survival rates over time, and Cox proportional hazards regression analysis will be used to compare hazards rates among treatments.

Summary statistics for categorical measures (including categorized continuous measures) will include sample size, frequency, and percentages. Logistic regression will be used to examine the treatment difference in binary efficacy outcomes if there is a need to adjust for covariate. Otherwise, Fisher’s exact test will be used to examine the treatment difference.

Summary statistics for discrete count measures will include sample size, mean, SD, median, minimum, and maximum.

Unless specified otherwise, baseline will be defined as the last available non-missing measurement during Visit 1 to Visit 3. For the safety related parameters, the definition of baseline and postbaseline are specified in [Table GPHK.6.2](#).

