6.13.1.1. Analysis Related to the Efficacy Estimand

The analysis related to efficacy estimand will be conducted utilizing data in the EAS.

For the mean percent body weight change from randomization, a MMRM will be conducted. Restricted maximum likelihood (REML) will be used to obtain model parameter estimates and the Kenward-Roger option will be used to estimate the denominator degrees of freedom. The response variable of MMRM will be the percent change in body weight from baseline values obtained at each scheduled post baseline visit.

For the percentage of participants achieving at least 5% body weight reduction from randomization over time, a logistic regression model will be used with the response variable of the percentage of participants achieving at least 5% body weight reduction at each scheduled postbaseline visit.

For MMRM the independent variables of analysis model is treatment group, visit, treatment-by-visit interaction, stratification factors (prediabetes status at randomization, sex and country/pooled country) as fixed effects, and baseline body weight as a covariate. An unstructured covariance structure will model relationship of within-patient errors. If this model fails to converge, the following variance covariance structures will be tested in order until convergence is achieved:

- heterogeneous Toeplitz
- heterogeneous first order autoregressive
- heterogeneous compound symmetry
- Toeplitz
- first order autoregressive, and
- compound symmetry.

The first covariance structure that converges will be used.

With the aid of the MMRM analysis, 2-sided 95% CIs for mean percent change in body weight from randomization to the 72-week visit for tirzepatide 10 mg and 15 mg compared to placebo will be derived and summarized. The resulting least squares mean (LSM) estimates of mean percent change in body weight from baseline will be plotted by visit and by study treatment.

A logistic regression model with terms of treatment group, country/pooled country, sex, and prediabetes status at randomization as fixed effects, and baseline body weight as a covariate, will be conducted for percentage of participants achieving at least 5% body weight reduction from randomization at the 72 week visit. Missing body weight measurement at 72 week will be imputed by the predicted value from MMRM model aforementioned, then the continuous measurements will be dichotomized into status of achieving at least 5% body weight reduction

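### The seven pooled-dose continuous key secondary comparisons are unbalanced 3:1 or 2:1 and make no allowance for arm SDs that differ, so their 95% intervals could be too narrow or too wide when the drug acts

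*SAP*

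**What the plan says.** Protocol 9.2 plans 2400 participants, 600 in each of four arms. SAP 6.13.2 (Table GPHK.6.4) pools doses for seven continuous key secondary endpoints:

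- All doses combined against placebo, 1800:600: "Mean change in triglycerides, HDL-C, non-HDL-C, SBP and fasting insulin from randomization at 72 weeks".
- 10 mg and 15 mg combined against placebo, 1200:600: weight change at Week 20 and SF-36v2 Physical Functioning at Week 72.

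Under the hybrid estimand all seven are analysed by ANCOVA. Under the efficacy estimand six use the MMRM of SAP 6.13.1.1, and SF-36 uses ANCOVA with LOCF. For the five endpoints with all doses combined, the table adds: "For hybrid estimand, missing data will be imputed first for each treatment based on Section 6.13.1.3, then combine all tirzepatide doses".

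On variance, SAP 6.13.1.1 says "An unstructured covariance structure will model relationship of within-patient errors", with Kenward-Roger degrees of freedom and a list of fallback structures. None of these is grouped by arm. The ANCOVA description in SAP 6.13.1.2 and the SF-36 row list only terms for the mean. No sandwich standard error or arm-specific variance is named anywhere. SAP 6.2 sets the nominal levels: "tests of treatment effects will be conducted at a 2-sided alpha level of 0.05" and "the confidence interval (CI) will be calculated at 95% 2-sided".

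**The concern.** A common-variance model weights the residual variance by group size, so at 3:1 three quarters of it comes from tirzepatide. The true standard error of the difference depends mostly on the smaller placebo group. If the two SDs differ, the model standard error is wrong, and imbalance makes the error larger.

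A difference in spread is plausible when the drug works. Triglycerides (mg/dL) and fasting insulin (pmol/L) are analysed as raw changes. If tirzepatide lowers them proportionally, it shrinks their SD and leaves placebo the more variable arm. Elsewhere the SAP log-transforms pancreatic enzymes (6.14.3.3.1) and the urinary albumin/creatinine ratio (6.14.3.14). In the other direction, pooling three doses, or mixing on-drug and off-drug data in the Full Analysis Set, can widen the tirzepatide SD.

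At stake are the confidence intervals reported for seven endpoints in the type 1 error strategy.

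**Working it through.** **Inputs.** From Protocol 9.2: 600 per arm, so k = 1800/600 = 3 or 1200/600 = 2. Dropout at an equal rate in every arm leaves k unchanged. From SAP 6.2: two-sided 0.05 and 95%. Assumed: r = SD placebo / SD tirzepatide. The only SD in the documents is "a common SD of 10"%, for percent weight change in the power calculation, and it says nothing about these seven endpoints.

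**The plan's own figure.** Protocol 9.2 states more than 90% power, "each at a 2-sided significance level of 0.025 using a 2-sample t-test". With 25% dropout there are 450 evaluable per arm. The standardised difference is 11 / (10 × √(2/450)) = 16.5, so power is effectively 100%, consistent with the claim. That comparison is 1:1. The pooled tests have no stated power, only the nominal level.

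**Formula.** Set the tirzepatide SD to 1, the placebo SD to r and the placebo group to n.

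- Model variance of the difference: [(k + r²)/(k + 1)] × (1/n) × (1 + 1/k)
- True variance: (1/n) × (r² + 1/k)
- Model SE / true SE = √[(k + r²)/(k r² + 1)]
- Coverage = 2Φ(1.96 × SE ratio) − 1

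For k = 3 and r = 1.2, √(4.44/5.32) = 0.914, and 1.96 × 0.914 = 1.79, which gives 92.7%.

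| r | SE ratio, 3:1 | Coverage, 3:1 | SE ratio, 2:1 | Coverage, 2:1 |
|---|---|---|---|---|
| 0.8 | 1.117 | 97.1% | 1.076 | 96.5% |
| 0.9 | 1.054 | 96.1% | 1.036 | 95.8% |
| 1.0 | 1.000 | 95.0% | 1.000 | 95.0% |
| 1.1 | 0.954 | 93.8% | 0.969 | 94.2% |
| 1.2 | 0.914 | 92.7% | 0.942 | 93.5% |
| 1.33 | 0.870 | 91.2% | 0.911 | 92.6% |
| 1.5 | 0.823 | 89.3% | 0.879 | 91.5% |

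For scale, a proportional fall of 1 − 1/1.2 = 17% relative to placebo would give r = 1.2, and one of 1 − 1/1.33 = 25% would give r = 1.33. These falls are illustrations, not figures from the plan.

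**Simulation check.** ANCOVA with one baseline covariate, complete data, equal means and 6000 runs per cell. At 1800:600, the common-variance test rejected in 3.1%, 4.7%, 7.2% and 10.7% of runs for r = 0.8, 1, 1.25 and 1.5. With HC3 robust standard errors the range was 4.7% to 5.2%. At 1200:600 the common-variance figures were 3.4%, 5.4%, 7.1% and 8.7%, and the robust range was 5.0% to 5.4%. Monte Carlo error is about 0.3 points.

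**By-dose contrasts.** A stand-alone 1:1 comparison has SE ratio 1 for every r. If all four arms share one model, a single-dose contrast has SE ratio √{2[(3 + r²)/4]/(1 + r²)}. That is 1.053 at r = 0.8 (coverage 96.1%) and 0.944 at r = 1.25 (93.6%). The combined 10 mg and 15 mg contrast in such a model has coverage 91.8% at r = 1.33, against 92.6% in its own two-group model. The SAP does not say which model is fitted.

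**The case against.** The tempting stronger reading is that the seven tests are mis-sized and that their type 1 error is inflated. The documents do not support it. They give no arm SD for any of these endpoints, and at equal SDs size and coverage are exactly nominal. A drug with no effect leaves both arms with the same distribution, so the test keeps its size. A proportional fall that shrinks the tirzepatide SD is itself a mean effect, so a significant result is then not a false positive. Inflation would need a drug that changes the spread and leaves the mean alone, and nothing in the plan suggests that. Coverage when the drug acts is what remains. With large effects, no significance decision may change.

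Other objections also have force:

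- Under the hybrid estimand, imputing by arm and applying Rubin's rules adds between-imputation variance that is specific to each arm, and this can repair part of the standard error. A simulation without covariates (3:1, r = 1.33, 25% missing, imputation from all observed data in the arm) gave 7.6% rejection, against 8.8% by the complete-data formula. With an assumed 30 retrieved dropouts per arm as donors, rejection fell to between 5.0% and 7.1%, depending on the set-up. The table is therefore towards the upper end for that estimand.
- The alpha for each pooled test is in Figure GPHK.6.1, which is not reproduced in the text available. The SE ratio does not depend on alpha.
- One residual variance is the standard reading of these models, not the SAP's wording.
- Changing the MMRM is not free. Empirical standard errors would displace Kenward-Roger. SBP has 10 post-baseline visits to Week 72, so an unstructured matrix has 10 × 11/2 = 55 parameters. This becomes 110 with two groups or 220 with four, and convergence failure becomes more likely.

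The last objection argues against replacing the main MMRM. It does not touch the ANCOVA.

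**Conclusion.** The point holds conditionally. The pooled comparisons are 3:1 or 2:1, and nothing in the SAP protects their intervals if arm SDs differ. The drift goes either way: too narrow if placebo is more variable, too wide if tirzepatide is. For SD ratios of 0.9 to 1.1 it is small, about one point of coverage at 3:1. It becomes material from about 1.2 upwards. The case for a ratio above 1 is strongest for triglycerides and insulin analysed as raw changes; for the other five endpoints there is no specific reason to expect placebo to be more variable. The figures rest on assumed SD ratios, a common SD across the tirzepatide doses and complete data. If one four-arm model is fitted, the by-dose contrasts share the problem. The plan contains no contradiction here; the reason to change it is that a safer standard error costs very little.

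**What to change.** - **ANCOVA (SAP 6.13.1.2 and Table GPHK.6.4).** Specify heteroscedasticity-robust (sandwich) standard errors, computed within each imputed data set before Rubin's rules. Apply the same to the SF-36 ANCOVA under both estimands.
- **MMRM (SAP 6.13.1.1).** Keep the Kenward-Roger analysis as the main one. Add a prespecified sensitivity analysis for the pooled comparisons, with treatment-group-specific covariance or empirical standard errors.
- **Model fitted.** State whether each pooled comparison is a two-group model or a contrast in a four-arm model.

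The cost is SAP wording, a model option and a little more analysis work. Intervals become slightly wider where placebo is more variable, narrower where tirzepatide is, and almost unchanged if the SDs are equal.
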